5.7.1.4. Phase Allocation of Adverse Events

Solicited events are always allocated to the respective Post Dose period.

Step 1: Allocation of events to the periods

Adverse events in the SDTM data base are allocated to periods based on their start date/time. If the start date/time of an event falls between (or on) the start and stop date/time of a period, the AE is attributed to that period (treatment-emergent principle).

- In case of partial start or stop dates (i.e. time and/or day and/or month and/or year missing), the events are allocated to the periods using the available partial information on start and end date; no imputation will be done. If, for instance, the AE start date only month and year are available, these data are compared to the month and year information of the periods. This rule may lead to multiplication of the event as a consequence of its assignment to multiple periods.
- In case of a completely missing end date, the date is imputed by the cut-off date of the analysis for participants still ongoing in the study, and by the end date of the last period for participants who discontinued or completed the trial. In case of a completely missing start date, the event is allocated to the first active vaccination regimen phase (post dose 1 period), except if the end date of the AE falls before the start of the first active vaccination regimen phase (post dose 1 period).

Step 2: Combination of events

Overlapping/consecutive events are defined as events of the same participant with the same preferred term which have at least 1 day overlap or for which the start date of an event is 1 day after the end date of the preceding event. Overlapping/consecutive events may be combined into one AE or not, according to the following rules:

1. If overlapping/consecutive events start in one of the following periods – Screening or post dose extension (i.e. non-active periods) – followed by an AE in – post-dose period (active period) – they are allocated to their respective periods and are considered as separate events.
2. In case overlapping/consecutive events start within a single period, they are considered as one and the same AE. The individual events which contribute to this AE are retained as individual records in the AdaM data base but are assigned the same onset, period, and total duration. All related attributes to the AE/phase/period should also be consistent with the new event.
3. In case overlapping/consecutive events start in both an active period followed by a non-active period, they are allocated to the active period only and are considered as one and the same AE. The individual events which contribute to this AE are retained as individual records in the AdaM data base but are assigned the same onset, vaccination regimen period, and total duration. All related attributes to the AE/phase/period should also be consistent with the new event.
4. In case an active period is followed by another active period, and the overlapping/consecutive events start in both periods, they are allocated to their respective period and are considered as separate AEs. The same rule applies for 2 non-active periods.

Remarks:

1. Events can only be combined into one and the same AE if their start and stop dates are known.
2. In case the completely missing end date is imputed (for period allocation), this date is also considered as a complete date.
3. Time is not considered when determining overlap of events.

5.7.1.5. Missing Data

Missing data will not be imputed. Participants who do not report an event/concomitant medication will be considered as participants without an event/concomitant medication. An AE with a missing severity or relationship will be considered as an AE reported, but will be considered as not reported for the severity or relationship. For example, an AE with missing severity will be considered as an AE reported for the analysis of any grade but will be considered as not reported for the analysis of at least grade 3.

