- n. After each vaccination, participants will remain under observation at the study site for at least 30 minutes (or longer if required by institutional/local practice) for the presence of any acute reactions and solicited events. Any solicited local (at injection site) and systemic AEs, unsolicited AEs, SAEs, concomitant medications, and vital signs will be documented by study-site personnel following this observation period and participants will be allowed to leave the study site after it is documented that the required minimum post-vaccination observation period is complete.
- o. Adverse events and special reporting situations that are related to study procedures or that are related to non-investigational sponsor products will be reported from the time a signed and dated ICF is obtained until the end of the study/early withdrawal. All other unsolicited AEs and special reporting situations will be reported for each vaccination from the time of vaccination until 28 days post-vaccination.
- p. MAAEs are to be reported for all participants from the moment of the first vaccination until 6 months after vaccination, except for MAAEs leading to study discontinuation which are to be reported during the entire study. New onset of chronic diseases will be collected as part of the MAAEs.
- q. All SAEs and AESIs related to study procedures or non-investigational sponsor products will be reported from the time a signed and dated ICF is obtained until the end of the study/early withdrawal. All other SAEs and AESIs are to be reported from the moment of vaccination until completion of the participant's last study-related procedure.

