Study-site personnel, as well as parents and caregivers, should be instructed how to interpret signs and symptoms (eg, crying and pain) in their individual child. They will be instructed to report both specific and nonspecific symptoms (including vomiting, diarrhea, sleepiness, variation in the intensity and pattern of crying, etc). These nonspecific symptoms may be the only manifestations of some adverse reaction observed in adolescents. Care should be taken that the clinical presentation of adverse reactions is not misinterpreted as the manifestation of a pre-existing or unrelated condition.

Moreover, symptoms that are dependent on participant communication ability (eg, nausea, pain, mood alterations) in younger or mentally-disabled adolescents could potentially be at risk for under- or mis-reporting.]

These events may or may not have been noted in the participant's reactogenicity diary.

Solicited Adverse Events

Solicited AEs are used to assess the reactogenicity of the study vaccine and are predefined local (at the injection site) and systemic events for which the participant is specifically questioned, and which are noted by participants in their reactogenicity diary.

After each vaccination, adolescents will remain under observation at the study site for at least 30 minutes (or longer if required by institutional/local practice) for the presence of any acute reactions and solicited events.

In addition, participants will record solicited signs and symptoms in a reactogenicity diary for 7 days post-vaccination. All participants will be provided with a reactogenicity diary and instructions on how to complete the reactogenicity diary (see Overview in Section 8). Reactogenicity diary information will be transferred to the sponsor. After review and verbal discussion of the initial reactogenicity diary entries with the participant, the investigator will

complete his/her own assessment in the relevant sections of the eCRF. Once a solicited sign or symptom from a reactogenicity diary is considered to be of severity Grade 1 or above, it will be recorded as a solicited AE.

Solicited Injection Site (Local) Adverse Events

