4. POPULATIONS (ANALYSIS SETS) FOR ANALYSIS

Analysis Sets	Description
Enrolled	All participants who sign the main ICF.
Randomized	The randomized analysis set includes all participants who were randomized in the study.
Full Analysis Set (FAS)	The Full Analysis Set will include all participants with at least one vaccine administration documented.

Analysis Sets	Description
Per Protocol Immunogenicity Set (PPI) ^a	The Per Protocol Immunogenicity population will include all randomized and vaccinated participants for whom immunogenicity data are available excluding data from participants with major protocol deviations expected to impact the immunogenicity outcomes (see details in Section 6.3). In addition, samples obtained after missed vaccinations, samples obtained from participants after SARS-CoV-2 infection (if confirmed by molecular testing or non-S-ELISA [or equivalent assay]), occurring during the study after randomization (if applicable), after other SARS-CoV-2 vaccination outside the study, and samples obtained outside pre-defined time windows will be excluded from the analysis set (see details in Sections 5.1.4 and 6.3).

^a If a participant is vaccinated out of window due to a study pause, this will not by default be a reason for excluding this participant from the PPI. Participants who were seronegative by local serology finger-prick test on Day 1 prior to study entry but were determined to be seropositive at baseline by central N- or S- serology testing will also be included (as the results from those assessments are not known prior to randomization).

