5.7.1. Adverse Events

5.7.1.1. Definitions

Solicited AEs are used to assess the reactogenicity of the study vaccine and are predefined local events (pain/tenderness, erythema, and swelling at the injection site) and systemic events (fatigue, headache, nausea, and myalgia, fever) for which the participant or parent(s)/caregiver(s) is specifically questioned, and which are noted by participants or parent(s)/caregiver(s) in their reactogenicity diary. Unsolicited AEs are all AEs for which the participant or parent(s)/caregiver(s) is not specifically questioned.

MAAEs are defined as AEs with medically-attended visits including hospital, emergency room, urgent care clinic, or other visits to or from medical personnel for any reason. Routine study visits will not be considered medically-attended visits. New onset of chronic diseases will be collected as part of the MAAEs. MAAEs are to be reported for all participants from the first vaccination until 6 months after each vaccination, except for MAAEs leading to study discontinuation which are to be reported during the entire study.

Solicited AEs shown in the tables are extracted from the investigator assessment pages (CE) of the CRF. Solicited administration site symptoms will by definition be considered as related to the study vaccine.

The following adverse events of special interest (AESI) will be collected in this study:

- Thrombosis with Thrombocytopenia Syndrome (TTS), defined as:
 - Thrombotic events: suspected deep vessel venous or arterial thrombotic events as detailed in CTP Section 10.14 and in Section [6.10](#)
 - Thrombocytopenia, defined as platelet count below 150,000/ μ L.
- Multisystem Inflammatory Syndrome in Children (MIS-C), defined as:
 - An individual aged <21 years presenting with fever^a, laboratory evidence of inflammation^b, and evidence of clinically severe illness requiring hospitalization, with multisystem (≥ 2)

^a Fever $>38.0^{\circ}\text{C}$ for ≥ 24 hours, or report of subjective fever lasting ≥ 24 hours.

^b Including, but not limited to, one or more of the following: an elevated C-reactive protein (CRP), erythrocyte sedimentation rate (ESR), fibrinogen, procalcitonin, D-dimer, ferritin, lactic acid dehydrogenase (LDH), or interleukin 6 (IL-6), elevated neutrophils, reduced lymphocytes, and low albumin.

- organ involvement (cardiac, renal, respiratory, hematologic, gastrointestinal, dermatologic, or neurological); AND
- No alternative plausible diagnoses; AND

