5.7.1.3. Analysis of Adverse Events

The number and percentage of participants with at least one particular AE (unsolicited/solicited) will be tabulated.

Unsolicited AEs will be summarized by System Organ Class and Preferred Term. Solicited AEs will be summarized by class (administration site, systemic) and preferred term.

For solicited AEs, the following tables will be provided: summary, by worst severity grade, at least grade 3, related (systemic only), at least grade 3 related, time to onset (in days) from the start of each vaccination period and duration (in days) for most frequent events (>5%) and body temperature. Note: Duration is defined as number of days from the start of the event until resolution of the event. The time to first onset is defined as (date of first onset – reference date + 1). The reference dates are the start dates of all prior vaccination periods (i.e. the prior vaccination dates for dose 1, dose 2 and/or Booster).

For unsolicited AEs, the following tables will be provided: summary table (including SAE, AESIs, MAAEs, MAAEs leading to study discontinuation, fatal outcome, and discontinuation), all events, most frequent (>5%), at least grade 3, related, at least grade 3 related, and SAE. The proportion of AEs resulting in a medically attended visit (other than routine health maintenance visits) will also be tabulated.

Selected tables will be repeated by SARS-CoV-2 by serostatus at baseline [or in seronegative subgroup only if there are less than 5% of seropositive subjects], and overall.

Listings and/or participant narratives will be provided as appropriate, for those participants who die, discontinue study due to an AE, experience a SAE, or AESI.

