For the grades, no distinction will be made between test results of samples obtained under fasting and under non-fasting conditions: in case limits under fasting and non-fasting conditions differ, the limits of the conditions (fasting/non-fasting) of scheduled visits as planned in the CTP will always be used, also for samples obtained under a different condition (e.g. samples of withdrawal visits).

Change from baseline in laboratory results (shift table based on toxicity grade) will be summarized by timepoint post vaccination.

A listing of participants with fever according to the FDA grading table will also be provided. In addition, temperature measurements (whether obtained from the diary or from on-site assessments) will be allocated to predefined temperature intervals (from 37.5° C until 40°C, in steps of half degree increments; e.g. <37.5, 37.5-<38, 38-<38.5, ... >40), and the worst temperature reported over the first 7 first days after a vaccination (Day1 to Day8, from any of the diary or the on-site assessments) will be tabulated by intervals.

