- A symptom (e.g. feeling generally unwell, fatigue, physical weakness, cough, etc.) is assumed to be present on each day the associated Yes/No question is answered “Yes” or the associated severity question has a rating > 0 .
- If the PRO was not completed due to the participant being too ill or due to the participant being hospitalized, the symptom will be considered present with maximum severity score. If the PRO was completed due to any other reason, no imputations will be done.

Duration of the episode will be calculated as (episode end date – episode start date) + 1. Duration of each symptom will be calculated as last date of symptom reporting – its first date + 1.

The following analyses will be conducted for confirmed SARS-CoV-2 infection cases:

- At the level of first episodes, the following statistics will be calculated: number of episodes, mean and median duration of episodes (with min, max, q1 and q3), and mean and median number of symptoms reported per episode (with min, max, q1 and q3).
- At the level of the symptoms for each first episode, the following statistics will be calculated: number of participants experiencing the symptom, mean and median duration of each symptom (with min, max, q1 and q3), median (with min, max, q1 and q3) of highest severity of each symptom, median duration of the highest severity of each symptom (with min, max, q1 and q3).
- At the level of the participants, for each episode and each symptom separately, the duration, and minimum and maximum severity scores will be tabulated (as available).

In addition, participant listings will be provided containing the SIC information for each time point. Details about these analyses will be provided in the DPS.

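### SAP 5.7.1.5 counts silence as no event for solicited AEs too, so a dosed participant with no diary or follow-up data lowers the reported rate unseen (minor)

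*SAP*

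**What the plan says.** SAP 5.7.1.5 is the only missing-data rule for adverse events. It opens by saying that nothing is imputed, then adds: "Participants who do not report an event/concomitant medication will be considered as participants without an event/concomitant medication". It sits under 5.7.1, which covers both kinds of AE. Section 5.7.1.3 says: "The number and percentage of participants with at least one particular AE (unsolicited/solicited) will be tabulated".

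Safety analyses use the FAS unless stated otherwise (SAP 5.1), and SAP 4 defines it this way: "The Full Analysis Set will include all participants with at least one vaccine administration documented". Section 5.4.3 asks for counts, percentages and exact intervals for binary variables, and gives no denominator rule for solicited AEs.

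On the source of the data, SAP 5.7.1.1 says: "Solicited AEs shown in the tables are extracted from the investigator assessment pages (CE) of the CRF". Under Protocol 8.3.2, once a diary sign or symptom "is considered to be of severity Grade 1 or above, it will be recorded as a solicited AE". Before going home, "participants will remain under observation at the study site for at least 30 minutes" (Protocol 1.3.1, footnote n), and any solicited AE seen in that time is documented. The rest of the 7-day window depends on the diary and its review by the investigator.

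Table layouts and programming instructions are left to the DPS (SAP 1).

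**The concern.** For unsolicited AEs, reading no report as no event is ordinary practice. Solicited AEs are different, because the participant is asked about each symptom daily for a week. Having been asked and reporting nothing is not the same state as having no data. Under the SAP text both states add one to the denominator and nothing to the numerator, and the table does not show which is which.

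The worst-temperature table in SAP 5.7.2 does not reveal the difference. It takes readings "from any of the diary or the on-site assessments", and the Schedule of Activities has a post-vaccination temperature at every vaccination visit, so a participant with no diary can still appear in it.

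Solicited AEs over 7 days are a primary endpoint after doses 1 and 2 and a secondary endpoint after the booster (SAP 1.1). At stake is an understatement of a descriptive safety rate that the reader of the table could not detect.

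**Working it through.** **Inputs.** N = 50 per group (SAP 1.2, Table 1); 100 when first-dose data are pooled by dose level (SAP 3, Table 2); about 15 aged 16 to 17 per group (30% of 50, SAP 1.2). The event counts and k0 are assumptions, since the documents give neither.

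**The plan's own precision figures.** SAP Table 2 reproduces with exact Clopper-Pearson 90% intervals. For zero events in 50 the upper limit is 1 − 0.05^(1/50) = 5.8%. For 50% observed the interval is 37.6% to 62.4%, width 24.8 points. For N = 100 the widths run from 3.0 to 17.3 points. The 5.8% is also the one-sided 95% limit in Protocol Table 5.

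**Range under the rule.** Let x be the participants with a recorded solicited AE, including any seen on site. Let k0 be the dosed participants with no solicited data after the on-site observation and no recorded solicited AE. Anyone with an on-site reaction and nothing later is already in x, so must not be in k0.

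- SAP rule: x/N, which is also the lower end (none of the k0 had an event)
- Upper end: (x + k0)/N (all of the k0 had an event)
- Assessed-only: x/(N − k0), if all x events fall in participants with later data

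For N = 50 and x = 10:

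| k0 | SAP rule | Assessed-only | Upper end |
|---|---|---|---|
| 0 | 10/50 = 20.0% | 10/50 = 20.0% | 10/50 = 20.0% |
| 1 | 20.0% | 10/49 = 20.4% | 11/50 = 22.0% |
| 2 | 20.0% | 10/48 = 20.8% | 12/50 = 24.0% |
| 5 | 20.0% | 10/45 = 22.2% | 15/50 = 30.0% |

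With a rarer outcome, x = 2, the SAP rule gives 4.0%. Assessed-only is 2/48 = 4.2% or 2/45 = 4.4% for k0 = 2 or 5, with upper ends 4/50 = 8.0% and 7/50 = 14.0%.

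**Against sampling error.** Exact 95% intervals are 10.0% to 33.7% for 10/50, 10.5% to 35.0% for 10/48 and 11.2% to 37.1% for 10/45. The move from all-vaccinated to assessed-only is small beside these.

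**Zero events.** The one-sided 95% upper limit is 1 − 0.05^(1/n): 5.8% for n = 50, 6.1% for n = 48 (6.05% before rounding) and 6.4% for n = 45.

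**Width of the range.** It is k0/N. Each such participant adds 2 points at N = 50, 1 point at N = 100 and 6.7 points at N = 15. Since SAP 5.1 asks for output by age group, the 16 to 17 columns are the most sensitive.

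**The case against.** The strongest case is that the documents give no sign that k0 exceeds zero. A safety visit follows 7 days after each dose, with another by 28 days. The investigator enters an assessment after discussing the diary, and a missed diary review moves to the next visit (Protocol 8 and 8.3.2). SAP 5.3 tabulates attendance by visit, so missed contacts are partly visible. The DPS could already define the denominator. SAP 5.7.1.5 also begins by ruling out imputation, so the next sentence might be meant only for people who were asked and had nothing to report. No test is planned, and swapping the main denominator of a primary safety endpoint after the sponsor is unblinded has its own cost.

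Most of this stands as a limit on size. It does not remove the point. The sentence about non-reporters is unrestricted and assigns them a value, whatever the sentence before it says, and the SAP text contains nothing narrower. The concern about swapping denominators is fair, which is why the planned rate should stay beside the new one.

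A reader might go further in two ways that the documents do not support:

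- **Precedent from the symptom questionnaire.** SAP 5.8.3 has a maximum-severity rule that begins "If the PRO was not completed due to the participant being too ill or due to the participant being hospitalized", which might suggest the SAP contradicts itself. That rule is tied to stated reasons within COVID-19 episodes, and nothing is imputed for other reasons. It sets no standard for vaccine diaries.
- **Effect on dose selection.** SAP 5.9.1 says that its guidelines will not be assessed in this study, and SAP 2 already refers to primary-analysis results. A change now cannot reach the dose-level determination tied to that analysis in SAP 5.9.

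**Conclusion.** The point holds as a minor one. As the SAP text stands, the solicited-AE rate is the lowest value compatible with the data whenever k0 is above zero, and the table does not show when that is so. In the assumed example of 10/50, the gap to the assessed-only rate is 0.8 points with k0 = 2 and 2.2 points with k0 = 5. The upper ends lie 4 and 10 points higher. With complete data the effect is nil.

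This rests on three things: reading 5.7.1.5 as reaching solicited AEs, from its position and unrestricted wording, since it does not name them; the DPS not having narrowed the denominator; and an unknown k0 that is probably small. The point covers only participants who received the dose in question. That reported rates are in fact biased cannot be established from these documents.

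What can still change is the final analysis. The primary analysis stops at 28 days post-dose 2 (SAP 5.9), so the post-booster tables for Groups 1 to 3 are first planned for the final analysis, unless an optional interim analysis has already reported them.

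**What to change.** For the final analysis, starting with the post-booster tables:

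1. In SAP 5.7.1.5, limit the rule that non-reporting means no event to unsolicited AEs and concomitant medication.
2. In each solicited-AE table, by group and dose, add a row with the number of dosed participants who have no solicited data after the on-site observation.
3. Keep the existing rate among all FAS participants who received that dose. Beside it, show an assessed-only rate. Its denominator is participants who received the dose and have either at least one diary day, or a completed post-vaccination visit or call at which solicited AEs were reviewed, whether or not any was found.
4. Keep on-site events in participants with no later data in the all-vaccinated rate and the listings. Leave these participants out of both numerator and denominator of the assessed-only rate. Admitting them only when they had an event would push the rate up by construction.

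The cost is a few sentences in the SAP, one flag, one row and one extra column of slightly different rates. Keeping the all-vaccinated rate preserves comparability with tables already produced. The assessed-only rate overstates if non-reporters are mostly symptom-free, and it does nothing about blank days within a diary that was started. If k0 turns out to be zero, the new row still documents completeness.

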9.4.2. Primary/Secondary Endpoints

Safety Endpoints

No formal statistical testing of safety data is planned. Safety data will be analyzed descriptively by vaccine group and by age group (12 to 15, and 16 to 17). In addition, for selected tables, tabulations pooled by vaccine dose will also be provided. All safety analyses will be done on the FAS.

Adverse Events

The verbatim terms used in the eCRF by investigators to identify AEs will be coded using the Medical Dictionary for Regulatory Activities (MedDRA). All reported AEs will be included in the analysis. (S)AEs caused by molecularly confirmed SARS-CoV-2 infection will be removed at the analysis level from the (S)AE listings and tables and presented separately. For each AE, the percentage of participants who experience at least one occurrence of the given event will be summarized by vaccine group.

Summaries, listings, datasets, or participant narratives may be provided, as appropriate, for those participants who die, who discontinue study vaccine due to an AE, or who experience a severe AE, AESI, or an SAE (including MIS-C).

Solicited local (at injection site) and systemic AEs will be summarized descriptively. The number and percentages of participants with at least one solicited local (at injection site) or systemic AE will be presented. The frequencies by vaccine group as well as frequencies according to severity and duration will be described for solicited AEs. Frequencies of unsolicited AEs, separately for all and vaccination-related only, will be presented by System Organ Class and preferred term, while those of solicited AEs will be presented only by preferred term.

Vital Signs

Vital signs including temperature, pulse/heart rate, preferably supine systolic and diastolic blood pressure, and respiratory rate will be summarized over time, using descriptive statistics and/or graphically. The percentage of participants with values beyond clinically important limits will be summarized.

Physical Examinations

Physical examination findings will be summarized at baseline. A listing of the abnormalities will be made.

Immunogenicity Endpoints

Descriptive statistics (geometric mean and confidence intervals, or median and interquartile range Q1-Q3, as appropriate) will be calculated for continuous immunologic parameters. Several

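### A missing severity or relationship entry can lower, but never raise, the Grade 3-or-worse and related adverse event rates, and the SAP plans nothing that bounds the effect

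*SAP*

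**What the plan says.** SAP 5.7.1.5 opens with "Missing data will not be imputed". On AE attributes it says: "An AE with a missing severity or relationship will be considered as an AE reported, but will be considered as not reported for the severity". The sentence goes on to apply the same treatment to relationship. The SAP's own example is an AE with no severity: it counts in the any-grade analysis but "will be considered as not reported for the analysis of at least grade 3".

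SAP 5.7.1.3 defines the unit: "The number and percentage of participants with at least one particular AE (unsolicited/solicited) will be tabulated". For unsolicited AEs the planned tables include "at least grade 3, related, at least grade 3 related, and SAE". Grade 3-or-worse and related tables are also planned for solicited AEs, with the plain related table limited to systemic events.

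Protocol 9.4.2 fixes the denominator: "All safety analyses will be done on the FAS". Nothing in SAP 5.7.1.5 removes a participant with an incomplete AE record from it.

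Two provisions limit the reach of the rule. SAP 5.7.1.1 states: "Solicited administration site symptoms will by definition be considered as related to the study vaccine". SAP 5.7.1.2 derives the severity of erythema and swelling from the diameter, and of fever from the temperature.

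**The concern.** In these tables a blank works as not Grade 3 or not related, although the event is known to have happened. That differs from a participant who reports nothing. The error in an absolute rate runs one way, and no planned sensitivity analysis or missing category shows how large it is.

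The SAP takes the cautious side for comparable safety gaps elsewhere:

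- An AE with a wholly missing start date goes to the post-dose 1 period unless its end date rules that out (5.7.1.4).
- An abnormality with no baseline value counts as emerging, and a laboratory value in a hole of the grading scale takes the worse adjacent grade (5.7.2).
- A symptom questionnaire left blank because the participant was too ill or hospitalized is scored at maximum severity (5.8.3).

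AE severity and causality take the opposite side, and no reason is given.

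The loss would also be hard to see. A by-grade table is planned for solicited AEs but not listed for unsolicited ones, and no listed table would reveal a missing relationship. Listings and narratives are promised for deaths, discontinuations due to an AE, SAEs and AESIs (5.7.1.3), so an unclassified non-serious AE need not appear in them.

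At stake are primary safety tables with about 50 participants per group, where severe or related unsolicited events may be few. SAP Section 3 says that the choice of regimen rests primarily on safety and reactogenicity. SAP 5.9 still plans a dose-level selection at the primary analysis. The current design has no placebo-only group, so absolute rates carry weight.

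**Working it through.** **Inputs.** N=50 per group, or 100 when groups with the same first dose are pooled (SAP Section 3 and 5.1.6). Binary variables get exact Clopper-Pearson intervals (SAP 5.4.3). Neither document gives a rate of missing severity or relationship, so every number of gaps below is an assumption.

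**Step 1: reproduce the plan's own figures.** SAP 5.7.1.5 states no number. The nearest is SAP Table 2, the 90% two-sided interval for an AE rate. With exact limits, and with 1 − 0.05^(1/N) as the upper limit at zero events:

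- N=50: 0 to 5.8% at an observed 0%; 37.6% to 62.4% at 50% (width 24.8).
- N=100: 0 to 3.0% at 0%; 41.4% to 58.6% at 50% (width 17.3 before the limits are rounded).

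All ten intervals in Table 2 reproduce.

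**Step 2: direction and maximum size.** Let x be the participants counted under the SAP rule. Let k be the participants not counted who have at least one AE that would count if its missing field were filled in the worst way.

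- SAP rate = x/N
- Worst-case rate = (x + k)/N

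Since k ≥ 0, the SAP rate never exceeds the worst-case rate. Each unit of k is worth 1/50 = 2.0 points, or 1/100 = 1.0 point when pooled. The true rate lies between the two. A gap costs nothing if the event was really Grade 1–2 or unrelated, or if the participant has another qualifying event, because the count is of participants.

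**Step 3: a small count.** Three participants have a truly severe event and one grade is missing. The table shows 2/50 = 4.0% (exact 95% CI 0.5–13.7%) instead of 3/50 = 6.0% (1.3–16.5%).

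**Step 4: a larger count.** The 20% starting rate is the SAP's assumed Grade 3 rate for the young-adult comparator (5.9.1), used here only as an illustration. Intervals are exact 90%.

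| k | From 10/50 | From 20/100 |
|---|---|---|
| 0 | 20% (11.3–31.6) | 20% (13.7–27.7) |
| 1 | 22% (12.9–33.8) | 21% (14.5–28.8) |
| 2 | 24% (14.5–36.0) | 22% (15.4–29.9) |
| 5 | 30% (19.5–42.4) | 25% (18.0–33.1) |

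**Step 5: expected loss.** Loss = p × m × (1 − q). Here p is the true rate, m the share of qualifying participants with a gap on a qualifying event, and q the chance that such a participant has another complete qualifying event.

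- p = 20%, q = 0: m = 5%, 10% or 20% gives a loss of 1.0, 2.0 or 4.0 points, so the observed rate is 19%, 18% or 16%.
- p = 20%, m = 10%, q = 0.5: the loss is 1.0 point, so the observed rate is 19%.
- m = 0: no loss.

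**Step 6: where the rule can bite.**

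| AE type | Missing severity | Missing relationship |
|---|---|---|
| Unsolicited | Yes | Yes |
| Solicited systemic | Little: fever is derived, the others are graded at entry (Protocol 8.3.2) | Yes |
| Solicited local | Little: erythema and swelling are derived, pain is graded at entry | No: related by definition |

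**The case against.** The strongest answer is that the gaps may hardly exist. Protocol 10.4.5 obliges investigators to record relationship in the eCRF. Protocol 10.4.3 has all AEs coded for severity. A solicited sign becomes a solicited AE only once it is judged Grade 1 or above (Protocol 8.3.2), so it should carry a grade. Related AEs of Grade 3 or above go to the sponsor within 24 hours (Protocol 6.8), and the eCRF is reviewed for completeness and queried (Protocol 10.3.8 and 10.3.9). These controls make gaps less likely without excluding them, and the SAP writes a rule for the case.

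Three stronger readings are tempting, and the documents do not support them.

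- A reader might infer that every gap lowers a rate. It does not, for the reasons in Step 2.
- A reader might infer that the rule always favours the vaccine. That holds for absolute rates only. The rule applies equally to all six groups, each of which starts with active vaccine. A between-group difference can move either way, depending on where the gaps fall.
- A reader might infer that one unclassified event could tip the dose decision. SAP 5.9.1 says that the Grade 3 go/no-go guidelines will not be assessed in this study, and no hypothesis is tested, so there is no numerical threshold to cross.

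It is also fair to say that the SAE, AESI, medically-attended, fatal and discontinuation summaries are not filtered by grade or relationship, and that the event stays in the any-grade table. Table layouts sit in the separate Data Presentation Specifications, which are not available here and might show a missing category. What can be said is that the SAP itself plans none.

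**Conclusion.** The point holds in a limited form. SAP 5.7.1.5 is an explicit rule whose effect on the absolute Grade 3-or-worse, related, and Grade 3-or-worse related rates is downward or nil, and the SAP plans nothing that bounds it. The shift per affected participant is at most 2 points at N=50 and 1 point at N=100. It is reached only when the event truly qualified and was the participant's only qualifying event. The exposure is mainly unsolicited AEs, plus the relationship of solicited systemic AEs.

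The total effect depends on the number of missing fields, which is unknown and may be zero. The point rests on the participant staying in the denominator, which follows from the FAS rule and the absence of any exclusion. It should be fixed because the remedy is cheap and the tables serve a primary objective. It does not show that the planned safety conclusions are wrong.

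**What to change.** Amend SAP 5.7.1.5 in three ways:

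1. Count an AE with missing relationship as related. Solicited local AEs need no change, since they are already related by definition.
2. Keep the current Grade 3-or-worse tables, including the related version, and add a worst-case version that counts an AE with missing severity as at least Grade 3.
3. Report, per group, the number of AEs with missing severity and the number with missing relationship, as a row or a footnote.

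The cost is a few SAP lines, a small programming change and the extra worst-case tables. The downside is a slight overstatement of related rates, and of severe rates in the worst-case version, when fields are missing. If all fields are complete, no rate changes and the counts in item 3 show that.
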